5. STUDY POPULATION

5.1. Sample size

The sample size for the present study was calculated with 90% power and a two-sided 0.05 significance level. At least 21 subjects would be needed for this study to find a significant increase in cytokine levels. Based on the 2007 study by Romeo et al. titled 'Changes in the Immune System after Moderate Beer Consumption', there was a significant increase in the cytokine IFNg in men comparing between a 30-day abstinence period and a 30-day moderate beer consumption period. From their data, the standard deviation of the difference between the two periods and the difference in their means was derived as 8287 pg/ml and 6208 pg/ml respectively. Using these values and a 90% power with 0.05 significance level, the minimum sample size was calculated to be 21. To account for a loss to follow-up, 30 subjects will be recruited for this study.

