6. STUDY DESIGN

6.1. Study method

The experimental design used in this study is a randomised, controlled, within-subject cross-over design. Each individual will undergo a 2-week intervention each of moderate beer consumption and moderate probiotic beer consumption, with a 1-week period of washout in between. The total study duration will be 5 weeks. According to the Health Promotion Board (HPB), the recommendation for safe alcohol consumption is two standard drinks a day for men. For beer, one standard drink is defined as one can of beer at 330ml. The beer used in this study is prepared at 330ml in one can (3.5-5% alcohol) in compliance with one standard beer drink. Only males will be recruited in this study, and they are to consume only one can of normal beer or probiotic beer per day during the study periods, which is within the safe moderate alcohol consumption standards set by HPB.

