7. STATISTICAL METHODS

We will utilise data from blood draws to find the change in C-reactive protein, white blood cell count, and cytokine panels from baseline after each study arm to derive summary statistics for each patient.

Data will be analysed using statistical software (eg. SPSS/Stata), with significance defined as *p*-value of less than 0.05 on a two-sided paired t-test. Other variables will be presented as

mean \pm SE. Differences between groups will be analysed using a mixed effect model which can also manage missing data and the presence of unforeseen carryover effects.

For any secondary measurements, paired-t test will also be used to assess baseline versus post-intervention outcomes, compared between the 2 intervention arms.

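### Section 7 says the mixed model can manage unforeseen carryover but states no carryover term or assumption, and the paired t-test that defines significance has neither a carryover nor a period term.

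*Combined protocol and SAP*

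**What the plan says.** Section 7 of the combined protocol and SAP takes, for each participant, the change in C-reactive protein, white blood cell count and "cytokine panels from baseline after each study arm to derive summary statistics for each patient". It defines significance as a p-value "less than 0.05 on a two-sided paired t-test". It then says that differences between groups will be analysed with a "mixed effect model which can also manage missing data and the presence of unforeseen carryover effects". It lists no fixed or random effects, no carryover term, no assumption about residual effects, and no rule for what happens if carryover is seen. For the remaining outcomes it says: "For any secondary measurements, paired-t test will also be used".

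The design features that bear on carryover are in section 6. Section 6.1 gives two 2-week interventions "with a 1-week period of washout in between", and section 6.4 takes a new pre-intervention blood sample at Visit 4. Section 7 does not connect either feature to the analysis. Section 6.2 assigns each of 30 sets at random to one of two sequences and does not say that the sequences will be equal in size.

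**The concern.** Section 7 credits the mixed model with a property that the plan as written does not give it. What a mixed model does about carryover depends on its terms and on what is assumed about residue at Visits 4 and 5, and the plan gives neither. Two analysts could both follow section 7, make different choices, and report different estimates from the same data. A reader would also take the result to be protected against carryover in general, when any protection depends on a condition the plan never states. The paired t-test has no carryover term, and it has no period term either, which matters separately if the sequences are unequal.

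**Working it through.** **1. The plan's own figure.** Section 5.1 gives the "standard deviation of the difference between the two periods and the difference in their means was derived as 8287 pg/ml and 6208 pg/ml", with 90% power and two-sided 0.05. For a paired t-test the standardised difference is 6208/8287 = 0.749. The noncentral t gives power 0.888 at n = 20 and 0.904 at n = 21, so the stated 21 reproduces. The sample size therefore rests on a plain within-person comparison.

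**2. What a carryover term does to change scores.** There are four cell means: probiotic-first in periods 1 and 2, then normal-first in periods 1 and 2. In that order the weights of the treatment estimate are:

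| Model (participant random) | Weights |
|---|---|
| Treatment + period | 0.5, -0.5, -0.5, 0.5 |
| Treatment + period + sequence | 0.5, -0.5, -0.5, 0.5 |
| Treatment + period + unrestricted carryover | 1, 0, -1, 0 |
| Treatment + period + sequence + carryover | not estimable |

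The first two rows correct nothing beyond what subtracting the baseline does. The third leaves only the between-person comparison in period 1. The fourth has 5 parameters (with the intercept) for 4 means, so its rank is 4. To check, code sequence as 1 for probiotic-first and carryover as 1 for probiotic-first in period 2. Add 0.5 to treatment and 1 to carryover, and take 0.5 from period and 0.5 from sequence. The four means move by 0.5 - 0.5, -0.5 - 0.5 + 1, 0, and 0.5 - 0.5. All are zero, so the data cannot tell the two sets of parameters apart.

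**3. When the estimate is unbiased.** Let fractions L4 and L5 of the probiotic effect D remain at Visits 4 and 5 in the probiotic-first sequence, with none from normal beer. These fractions are assumed; the documents give none.
- Change from each period's own baseline (Visit 4 as the period-2 baseline): the probiotic-first period-2 change shifts by (L5 - L4)D. With weight -0.5 the estimate becomes D × [1 + (L4 - L5)/2].
- Post-values only: the shift is L5 × D, and the estimate becomes D × [1 - L5/2].

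| L4 | L5 | Change contrast | Post-value contrast |
|---|---|---|---|
| 0.25 | 0 | +12.5% | 0% |
| 0.5 | 0 | +25% | 0% |
| 0.5 | 0.25 | +12.5% | -12.5% |
| 0.5 | 0.5 | 0% | -25% |

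The change contrast needs L4 = L5; the post-value contrast needs L5 = 0. If Visit 2 were the baseline for both periods, it would cancel within person and the post-value column would apply.

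**4. Period effect and unequal sequences.** The paired mean difference picks up the period effect times (difference in sequence sizes)/N. At 18:12 this is 6/30 = 20%. If allocation is simple (an assumption), the binomial chance of 18:12 or worse is 36%, and of exactly 15:15 is 14%.

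**5. Precision of the change contrast.** Under compound symmetry with variance σ² and correlation ρ, a participant's difference between two post-values has variance 2σ²(1 - ρ), and between two changes 4σ²(1 - ρ), which is twice as large. If 8287 is the SD of a post-value difference, the SD for changes is 8287 × √2 = 11,720. Power for 6208, two-sided 0.05:

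| Participants | Post-values | Changes |
|---|---|---|
| 30 | 97.7% | 80% |
| 21 | 90% | 63% |

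These are illustrations. The 6208 comes from "comparing between a 30-day abstinence period and a 30-day moderate beer consumption period", so power for probiotic against normal beer is unknown.

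**6. What the Visit 4 baseline can show.** Compare Visit 4 minus Visit 2 between sequences, assuming SD 8287 and 15 per sequence (28 df). The 95% half-width is 2.048 × 8287 × √(2/15) = 6198 pg/ml, and power to detect 3104 (half of 6208) is 17%.

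**The case against.** The strongest reply is that the plan already has real protection. There is a washout, a fresh sample is taken at Visit 4, and change from that sample cancels any residue that is equal at Visits 4 and 5. This stands. A reader might infer that the analysis has no protection at all, and the last row of the bias table shows otherwise. In a model of Visits 2 to 5 together, without a carryover term and under compound symmetry, Visit 4 gets zero weight, so a residue confined to Visit 4 would do no harm. Section 7 also says only that the model can manage carryover, and with four blood samples some carryover models are estimable. But each works under a particular assumption, and the plan states none.

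Three other stronger readings are tempting.
- That carryover is present, or the washout too short: the documents give no evidence on either.
- That the paired t-test decides the comparison between beers: section 7 defines significance by it but assigns differences between groups to the mixed model, so which one decides is unclear.
- That carryover is the reason to replace the paired t-test: with balanced, complete data the period-adjusted model of change gives the same estimate. The case for replacement is period effects, possibly unequal sequences and incomplete data.

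**Conclusion.** The concern holds as a stated property that the plan does not deliver. Naming a mixed model does not manage carryover in this design, and section 7 gives neither the terms nor the assumption on which any protection would depend. The identifiability result (rank 4 of 5) needs no outside assumption. The bias of -25% to +25% rests on assumed residual fractions of up to one half, and its sign depends on which outcome is used. The power figures rest on compound symmetry, on one reading of 8287, and on an effect size from a different comparison. The change should be made before analysis; it does not call the design into question.

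**What to change.** - Delete the general statement that the model manages carryover.
- Name one decisive analysis for the blood immune markers: a mixed model of the change from each period's own baseline (Visits 2 and 4), with treatment, period and sequence fixed and participant random. Give the reasons for replacing the paired t-test as period effects, possibly unequal sequences and incomplete data.
- State that the model has no carryover term, that it assumes any residue is absent or equal at Visits 4 and 5, and that no carryover pre-test selects the analysis.
- Report two fixed sensitivity analyses that never replace the primary: a post-value analysis that does not use Visit 4, and a period-1-only estimate adjusted for Visit 2.
- Show Visit 4 minus Visit 2 by sequence with 95% confidence intervals, as description only. State its imprecision, and that a null result does not show carryover to be absent.

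The cost is SAP wording and a few tables from blood already planned at Visits 2 to 5. Two downsides should be disclosed. The assumption becomes explicit and the checks cannot prove it. The change outcome, which section 7 already chose, may also carry twice the variance of post-values, and under the reading above power at the minimum in section 5.1 ("At least 21 subjects would be needed for this study") would be about 63% rather than 90%.

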3. HYPOTHESIS AND OBJECTIVE

3.1. Hypothesis

The moderate consumption of probiotic beer is hypothesised to improve gut health and immunological parameters.

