6.3. Run-in period

Before each study visit, participants will be informed by the research personnel on the following study requirements:

1. Fast for 10-12 hours prior to reporting for the study visit.
2. Avoid foods high in fat (e.g. fried food) for 24 hours prior to reporting for the study visit.
3. Avoid caffeinated beverages 4-6 hours before reporting for the study visit.
4. Avoid strenuous exercises 24 hours prior to reporting for the study visit.

Subjects are also required to abstain from alcohol and probiotic-containing foods, drinks, or supplements for one week prior to the commencement of the study and during the course of

the study itself. No other alcohol and probiotic-containing foods should be consumed apart from the beer or probiotic beer provided during this duration.

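### The secondary-outcome sentence in Section 7 leaves the tested contrast open, and one of its two readings cannot separate the probiotic from the return to alcohol

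*Combined protocol and SAP*

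**What the plan says.** Section 7 has three statements that bear on the point.

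- The data are reduced to changes in C-reactive protein, white cell count and "cytokine panels from baseline after each study arm to derive summary statistics for each patient". Significance is a p-value "of less than 0.05 on a two-sided paired t-test", with no contrast named.
- "Differences between groups will be analysed using a mixed effect model which can also manage missing data".
- For secondary measurements, which the section does not list, a "paired-t test will also be used to assess baseline versus post-intervention outcomes, compared between the 2 intervention arms".

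The hypothesis in Section 3.1 has no comparator: "The moderate consumption of probiotic beer is hypothesised to improve gut health and immunological parameters". Sections 2.4, 6.1 and 6.2, in contrast, describe a randomised within-subject crossover of probiotic beer against normal beer.

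On the state of participants at each baseline, Section 6.3 requires abstinence from alcohol and probiotics "for one week prior to the commencement of the study" and allows only the study beers after that. Section 6.4 places a one-week washout between Visits 3 and 4. Each post sample is taken after 14 days of one can daily.

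**The concern.** In the secondary-outcome sentence, what the paired t-test is said to assess is before against after. The closing clause brings in the two arms but not the form of the comparison. It could be a single test on the two changes, or two separate tests whose results are then put next to each other. Because group differences are assigned to the mixed model in the preceding paragraph, an analyst could reasonably conclude that the paired t-test is left for within-beer changes. Under the hypothesis as worded in Section 3.1, a significant change on probiotic beer alone would appear to confirm it.

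In this design a within-beer change has at least three components: going from an alcohol-free week to daily beer, drift over the two weeks, and the probiotic. Section 5.1 itself relies on a significant IFNg rise in men, "comparing between a 30-day abstinence period and a 30-day moderate beer consumption period", with ordinary beer. A benefit could therefore be reported for probiotic beer that normal beer gives equally. Nor is significance on one beer and not on the other a test of the difference between them.

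**Working it through.** **Inputs from the documents.** Section 5.1: mean difference 6208 pg/ml, SD of the difference 8287 pg/ml, two-sided 0.05, 90% power, minimum 21, recruitment 30. Sections 6.3 and 6.4: an alcohol-free week before each baseline, 14 days of beer before each post sample.

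**Assumptions.** No probiotic effect; the same alcohol effect on both beers; normally distributed changes with SD 1; shared standardised change 0.25, 0.50 or 0.749; correlation between a participant's two changes 0 or 0.5. The documents give none of these for any secondary outcome.

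**Step 1: reproduce the plan's figure.** d = 6208/8287 = 0.749. Power of a two-sided paired t-test from the noncentral t distribution, with n − 1 degrees of freedom and noncentrality d√n, is 88.8% at n = 20 and 90.4% at n = 21. The minimum is 21, as stated. At n = 30 power is 97.7%.

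**Step 2: what each reading tests.** Write A for the alcohol effect, T for drift within a period and P for the probiotic effect.

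- Mean change on normal beer: A + T
- Mean change on probiotic beer: A + T + P
- Within-probiotic test: null hypothesis A + T + P = 0
- Between-beer test of changes: null hypothesis P = 0

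A cancels only in the between-beer test, and only if the two beers have the same strength. Section 2.2 gives a range of 3.5–5%.

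**Step 3: set P = 0.** If the shared change equals the planning effect, the chance that the within-probiotic test is significant is simply the power in Step 1: about 90% at n = 21 and 98% at n = 30.

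**Step 4: results set side by side.** If the two changes are independent and each test is significant with probability p, the chance that only probiotic beer is significant is p(1 − p). At the full planning effect this is 0.904 × 0.096 = 0.087 at n = 21 and 0.977 × 0.023 = 0.022 at n = 30. A simulation with 40,000 replicates per scenario extends this to smaller effects and correlated changes (each pair of figures is for correlation 0 / 0.5):

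| n | Shared change (SD units) | Probiotic-beer test significant | Significant on probiotic beer only |
|---|---|---|---|
| 21 | 0.25 | 19.5% / 19.1% | 15.8% / 11.3% |
| 21 | 0.50 | 59.0% / 59.3% | 24.4% / 16.6% |
| 21 | 0.749 | 90.4% / 90.6% | 8.6% / 6.9% |
| 30 | 0.25 | 26.2% / 26.2% | 19.5% / 13.5% |
| 30 | 0.50 | 75.1% / 75.5% | 18.6% / 13.0% |
| 30 | 0.749 | 97.8% / 97.8% | 2.2% / 1.9% |

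The between-beer paired test of changes was significant in 4.9% to 5.1% of replicates in every row.

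**Step 5: the valid reading.** Let D be a participant's probiotic-minus-normal difference in changes, and π the second-minus-first period effect. The expected D is P − π for those given probiotic beer first and P + π for the others. With sequence sizes m₁ (probiotic first) and m₂, the mean of D is P + π(m₂ − m₁)/(m₁ + m₂). The period term drops out of the mean only when the sequences are equal in size, which Section 6.2 does not state. Even then it adds to the variance of D. A plain paired t-test has no term for it, and it drops anyone with an incomplete period.

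**The case against.** The best defence is the sentence itself, which ends by calling for a comparison between the arms. Nothing in Section 7 says that p-values or significance verdicts are to be compared. The mixed-model statement is not limited to the main outcomes, and Sections 2.4, 6.1 and 6.2 make normal beer the randomised comparator. Sections 2.1 and 4.2 also frame the product as an alternative to normal beer. On this evidence the between-beer reading is at least as natural as the other, and under it the shared alcohol effect cancels for beers of equal strength.

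That part stands. A reader might infer that the plan does test secondary outcomes within each beer, so that the effect of resuming alcohol will be reported as a probiotic effect. The documents do not support this: it ignores the closing clause and predicts a report that no passage calls for.

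The figures are also open to challenge. The planning effect is for IFNg, a cytokine covered by the first paragraph of Section 7, and it comes from 30-day periods rather than one week followed by 14 days. At that full effect and n = 30, significance on probiotic beer alone occurs in only about 2% of trials. These limits are accepted, and the figures are illustrations only.

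The defence shows that a between-beer comparison is intended somewhere. It does not show that secondary outcomes rest on it, or that within-beer p-values carry no weight.

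**Conclusion.** The concern holds as an ambiguity. One reading of the sentence is valid; the other is not, because of where the baselines fall.

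Conditional on the within-beer reading, and on an alcohol effect as large as the IFNg planning effect, the probiotic-beer test would be significant in about 90% (n = 21) to 98% (n = 30) of trials with no probiotic effect. The side-by-side reading would mislead in about 7–24% of trials at n = 21 and 2–20% at n = 30, depending on the assumed shared effect and correlation. Under the between-beer reading these errors disappear and the rate is about 5%. What remains on that reading is the missing period term and the loss of participants with an incomplete period.

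A reader might also infer that the sample size or significance level is wrong. This point does not show that: the minimum of 21 reproduces exactly. Whether an effect from abstinence against beer is informative about power for probiotic against normal beer is a separate question.

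**What to change.** Replace the secondary-outcome sentence in Section 7 with text such as:

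> Each secondary outcome is tested by the probiotic-minus-normal contrast in change from the baseline of the same period. The contrast is estimated in the mixed model planned for group differences, with fixed terms for beer and period and a random participant effect. Within-beer changes are shown descriptively and are not taken as evidence of a probiotic effect.

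Reword Section 3.1 so that the improvement is claimed relative to the same daily amount of normal beer.

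The cost is two sentences. No new data are needed, and neither the sample size nor the significance level changes. With complete data the model is in effect the paired comparison adjusted for period, at the price of one degree of freedom; with a missing period it can still use the participant's other period. All that is given up is the use of within-beer p-values as evidence, and they cannot answer the trial's question. If the sponsor already meant the between-beer contrast, the edit records that intention before the data are analysed.

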8. SAFETY MEASUREMENTS

8.1. Definitions

8.1.1. Serious adverse event

A '*serious adverse event*' refers to any event that:

- Results in death
- Is life-threatening
- Requires hospitalization or prolongs existing hospitalization
- Results in a congenital anomaly
- Causes permanent disability or requires medical or surgical intervention to prevent permanent disability
- An important medical event that, based upon appropriate medical judgment, requires medical or surgical intervention to prevent one of the outcomes listed above.

8.1.2. Non-serious adverse event

'*Non-serious adverse event*' refers to any undesirable symptom or occurrence a subject experiences during participation in a clinical study that does not meet the "serious" criteria listed above.

8.1.3. Anticipated event

'*Anticipated event*' refers to any event attributed to the underlying condition of the patient being studied, or event attributed to the patient population being studied, or an adverse event anticipated on the basis of prior experience with the procedure and medication.

8.1.4. Unanticipated event

'*Unanticipated event*' refers to any unanticipated event that cannot be attributed to the underlying condition of the subject being studied or to the subject population, expected events whose frequency or severity exceeds what was anticipated, an event that cannot be attributed to a co-morbid condition or concomitant medication, or an adverse event that was not anticipated on the basis of prior experience with the procedures or drugs used in the study.

8.1.5. Related or possibly related event

‘Related event’ refers to any event directly or indirectly attributed to the procedure, medication and/or study participation, or events occurring with sufficient frequency to suggest that they are not random.

‘Possibly related event’ refers to any event with a reasonable possibility that the incident, experience, or outcome may have been caused by the procedures involved in the research.

8.1.6. Unrelated event

‘Unrelated event’ refers to any event that would occur regardless of study participation or events that are clearly random occurrences. If the frequency of the event suggests a possible connection to the study procedure, then it should be considered related.

8.2. Collecting, recording and reporting of “Unanticipated Problems Involving Risk to Subjects or Others” – UPIRTSO events to the National Health Group (NHG) Domain Specific Review Boards (DSRB)

UPIRTSO events refers to any incident, experience, or outcome, including adverse events, that meets ALL of the following criteria:

1. Unexpected

Any event occurred that is not consistent with the research procedures as described in the protocol-related documents (i.e., DSRB approved research protocol and informed consent document) or with the characteristics of the subject population being studied in terms of nature, severity and frequency.

2. Related or possibly related to participation in the research

Related, meaning any event directly or indirectly attributed to the procedure, medication and/or study participation, or events occurring with sufficient frequency to suggest that they are not random;

Possibly related, meaning any event with a reasonable possibility that the incident, experience, or outcome may have been caused by the procedures involved in the research.

3. Risk of harm

The research places participants or others at a greater risk of harm (including physical, psychological, economic, or social harm) than was previously known or recognized.

Reporting Timeline of UPIRTSO events to NHG DSRB:

- 1. Urgent Reporting:** All problems involving local deaths, whether related or not, should be reported immediately, within 24 hours after first knowledge by the NHG investigator.
- 2. Expedited Reporting:** All other problems must be reported as soon as possible but not later than 7 calendar days after first knowledge by the NHG investigator.

8.3. Collecting, recording and reporting of Expected Serious Adverse Events (SAEs) to the National Healthcare Group (NHG) Domain Specific Review Boards (DSRB) and Research Institution(s) (RI)

For reporting of **Expected SAEs**, ALL of the following have to be met:

1. Serious adverse event

A ‘serious adverse event’ refers to any event that:

- Results in death
- Is life-threatening
- Requires hospitalization or prolongs existing hospitalization
- Results in a congenital anomaly
- Causes permanent disability or requires medical or surgical intervention to prevent permanent disability
- An important medical event that, based upon appropriate medical judgment, requires medical or surgical intervention to prevent one of the outcomes listed above.

2. Expected event

Any risks or events reported that is listed in in the protocol-related documents (i.e., DSRB approved research protocol and informed consent document).

3. Related or possibly related to participation in the research

Related, meaning any event directly or indirectly attributed to the procedure, medication and/or study participation, or events occurring with sufficient frequency to suggest that they are not random;

Possibly related, meaning any event with a reasonable possibility that the incident, experience, or outcome may have been caused by the procedures involved in the research.

Reporting Timeline of Expected SAEs to NHG DSRB:

All Expected SAEs should be reported as soon as possible but no later than 7 calendar days after first knowledge by the investigator. Any additional relevant information about the events should be reported within 8 calendar days of making the initial report.

